Date: November 11, 2025

Study Title: Enhancing Treatment of Hoarding Disorder With Personalized In-Home Sorting and Decluttering Practice

NCT02843308

Scientific background:

Hoarding disorder (HD) is characterized by persistent difficulties parting with possessions, associated distress, and clutter that compromises the intended use of living spaces (American Psychiatric Association, 2022). HD is common, with an estimated overall pooled prevalence of 2.5% of the general population (Postlethwaite et al., 2019). HD causes significant impacts on social, occupational, and other important areas of functioning and health risks include falls and other injuries due to clutter (American Psychiatric Association, 2022). In severe cases, home fires and pest infestation extend health and safety risks to neighbors (Frost et al., 2000). HD is associated with significantly lower quality of life, social isolation, and high rate of co-occurring mental disorders (Frost et al., 2011a; Ong et al., 2015; Saxena et al., 2011; Tolin et al., 2019). Cognitive behavioral therapy (CBT) for hoarding symptoms has shown promise when delivered by a trained therapist in either individual or group settings (Tolin et al., 2015); however, cost and access to a therapist may be barriers for some (Thompson et al., 2017). One alternative is the Buried in Treasures [BIT] Workshop, an evidence-based, highly structured, short-term, skills-based group using CBT principles but led by peers (Frost et al., 2012a) or non-professional facilitators (Frost et al., 2011a). To date, studies have shown BIT can significantly reduce hoarding symptoms when compared to a waitlist control (Frost et al., 2012a) and is as effective as psychologist-led group CBT (Mathews et al., 2016). Despite these promising results, many continue to have impairing symptoms after treatment and high levels of clutter, regardless of modality or type of facilitator (Moulding et al., 2017; Tolin et al., 2015) and under-utilize HD treatments and services (Frost et al., 2012b). Approaches that enhance the clinical effects of these interventions are needed. Based on two studies—one reporting that personalized care and accountability made treatments more acceptable to individuals with hoarding disorder (Rodriguez et al., 2016) and another reporting that greater number of home sessions were associated with better clinical outcomes (Tolin et al., 2015)—we tested the feasibility and effectiveness of adding personalized, in-home uncluttering sessions to the final weeks of BIT with up to 20 hours of supervised in-home uncluttering practices in a small (N = 5) pilot study of BIT+ (Linkovski et al., 2018). Reductions in hoarding symptoms, clutter, and impairment of daily activities were observed. Treatment response rate was comparable to rates in other BIT studies, with continued improvement in clutter level after in-home uncluttering sessions (Linkovski et al., 2018). Although the pilot study of BIT+ was promising, it had limitations including the small sample size and open-label design. To build upon this small pilot, we tested BIT+ in a larger sample using a randomized waitlist-controlled trial design and hypothesized that individuals randomized to BIT+ would have more significant and more substantial benefits on hoarding symptoms than patients randomized to an 18-week long waitlist. After the waitlist, participants were offered BIT+, and the BIT+ completer sample was pooled to allow us sufficient sample size to estimate clinical benefits.

Objectives:

To test BIT+ in a larger sample using a randomized waitlist-controlled trial design; we hypothesize that individuals randomized to BIT+ will have more significant and more substantial benefits on hoarding symptoms than patients randomized to an 18-week long waitlist.

Design:

This randomized waitlist-controlled trial with 1:1 (BIT+ intervention; waitlist control) allocation was conducted at an academic outpatient research setting. Potential participants were recruited via study advertisements posted online and in the local community, radio ads, and by referrals from mental health professionals and local hoarding task forces between October 2016 and June 2019. The study protocol was approved by the Stanford Institutional Review Board (IRB), and participants provided written informed consent. The trial was prospectively registered; clinicaltrials.gov identifier: NCT02843308. Participants were randomized by group, employing random permuted blocks within a 1:1 allocation ratio between intervention and waitlist control groups. The group therapy facilitators could not be blinded to allocation for practical reasons; the independent evaluators who assessed home clutter levels were blinded to allocation. Although several trial designs (with an active comparator) were considered, limited resources prohibited these options. A waitlist-controlled trial design was selected given treatment could be delivered to all participants, while controlling for passage of time and allowing comparison to a prior study of BIT that also employed a waitlist control condition (Frost et al., 2012a).

Methods:

a) Inclusion and Exclusion Criteria

Eligible adults (ages 18–70) had a primary diagnosis of HD according to DSM-5 criteria (American Psychiatric Association, 2013) as assessed via structured clinical interview (SCID) (First et al., 2015), with clinically significant hoarding disorder (Saving Inventory-Revised [SI-R] ≥ 41) (Frost et al., 2012b), clutter that impaired living spaces (Clutter Image Rating [CIR] ≥ 4) (Frost et al., 2008), no or stable psychotropic medication use (defined as medication doses unchanged for >4 weeks prior to assessment or > 8 weeks if fluoxetine). Potential participants were excluded if they lived greater than 30 miles from Stanford University (because the study necessitated home visits), had OCD as a primary diagnosis, a current or history of psychotic disorder or bipolar disorder, a current eating disorder, a current moderate or lifetime severe substance use disorder or were severely depressed (Hamilton Depression Rating Scale >30) (Hamilton, 1960), at risk of suicide (Columbia-Suicide Severity Rating Scale ≥ 4) (Posner et al., 2011) or any other medical or neuropsychiatric condition increased risk of participation or would prevent completion of study procedures. Additionally, we excluded participants who were unwilling to have unclutter volunteers enter their home, were unable to follow study procedures, had clutter levels with the potential for objects falling from overhead (CIR >8 ; approximately above shoulder height or higher), had evidence of animal hoarding or pest infestation, or were at high risk of eviction due to legal proceedings that necessitated a higher level of care. Individuals who had started working with a professional organizer or cognitive behavior therapist for HD within 8 weeks of enrollment were also excluded.

b) Procedures

Participants made 20 study-related visits to the study site: a baseline visit at the study start, 18 weekly visits for the BIT+ intervention, and a close-out visit at the study's completion. The BIT+ intervention consisted of 16 weekly group BIT workshop and 20 h of in-home uncluttering sessions over 18 weeks. The study procedures were identical to the pilot study (Linkovski et al., 2018), with two exceptions based on participant feedback and expert input from [name]: a) rather than including a one-week break during Week 9 and a two-week break during Weeks 16–17, we continued weekly meeting uninterrupted to improve consistency; b) instead of concentrating the uncluttering at the end of the study with four weeks of twice weekly uncluttering, we slowly titrated up the duration and intensity over the last eight weeks to build up uncluttering stamina. The BIT workshop sessions are 2 hours long and structured based on the book, *Buried in Treasures: Help for Compulsive Acquiring, Saving and Hoarding* (Tolin et al., 2014) and the BIT facilitator's guide (Shuer and Frost, 2016). Each session was led by two trained, non-professional group facilitators and include HD-specific psycho-education, identifying acquisition triggers, tolerating urges to acquire, and developing skills for parting with possessions, following the methods of Frost et al. (2012a). For the uncluttering sessions, pairs of trained non-professional uncluttering volunteers made weekly home visits to each participant's residence for 10 visits of 2 hours each (20 hours of in-home uncluttering sessions over 18 weeks). The content of the sessions closely modeled content that participants learned during the BIT workshop and included the structured exercises detailed in the *Buried in Treasures* workbook (Tolin et al., 2014) and the BIT facilitator's guide (Shuer and Frost, 2016). As described previously (Linkovski et al., 2018), each session included a check-in, facilitated uncluttering time, and a closing in which participants shared their reflections and their objectives for the coming week.

Statistical Plan (including considerations for analysis):

Baseline variables will be assessed using descriptive statistics for the BIT+ and waitlist groups using means and standard deviations for the continuous, and frequencies and percentages for categorical variables.

We will employ standard linear mixed effects modeling (e.g., Bryk and Raudenbush, 2002; Singer and Willett, 2003) to estimate and compare the change from the pre-to post-treatment assessment during the first segment of our study in line with the intention to treat principle. The use of mixed effects modeling was chosen because this approach is better at handling missing data and yields improved power compared to linear regression. Specifically, we used a random intercept model assuming linear change. We will use maximum likelihood estimation with robust standard errors implemented in Mplus Version 8.4 (Muthén & Muthén, 1998–2017). Data points that are missing due to subject attrition will be handled assuming that data are missing at random (MAR; Little and Rubin, 2019) conditional on observed information. In our mixed effects analyses, the change (slope) in the outcome will be modeled as the key dependent variable predicted by the treatment assignment status. In particular, the change in SI-R total from baseline to end of treatment will be assessed. Specifically, will report the number of participants who met and exceeded the response criteria of the SI-R total (SI-R reduction ≥ 14 points).

In all analyses, we will use the nominal significance level ($\alpha = 0.05$). We will not adjust the significance level for multiple testing given that we had one clear primary endpoint. We will analyze several secondary outcomes including subscales of SI-R. We applied the same analytical strategy to analyze the data from the second segment of our study, where the individuals assigned to the waitlist condition

receives BIT+. Additionally, we will compare the first and second segments in terms of the estimated changes under BIT+ treatment.

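### Allocation and treatment are by group, but the analysis names no group effect or cluster; if SI-R change correlates within groups, intervals are too narrow and 0.05 is not held

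*Combined protocol and SAP*

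**What the plan says.** On allocation, the Design section states: "Participants were randomized by group, employing random permuted blocks within a 1:1 allocation ratio between intervention and waitlist control groups". The Objectives use different language: "we hypothesize that individuals randomized to BIT+ will have more significant and more substantial benefits on hoarding symptoms". The documents do not say whether whole groups or single participants were allocated, or how many groups there were and of what size.

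On delivery, Methods b) Procedures describes 16 weekly workshops given to groups, plus 20 hours of individual home sessions. Of the workshops it says: "Each session was led by two trained, non-professional group facilitators".

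On analysis, the Statistical Plan states: "Specifically, we used a random intercept model assuming linear change". The level of that intercept is not named. The only predictor of change is the arm: "the change (slope) in the outcome will be modeled as the key dependent variable predicted by the treatment assignment status". On estimation: "We will use maximum likelihood estimation with robust standard errors implemented in Mplus Version 8.4", with no cluster variable given. The same strategy is applied to the second segment, when the waitlist arm receives BIT+, and then "we will compare the first and second segments in terms of the estimated changes under BIT+ treatment". The threshold of 0.05 applies throughout: "In all analyses, we will use the nominal significance level".

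**The concern.** Members of a workshop group share facilitators, sessions and each other's company for months. Their SI-R changes may therefore be more alike than those of members of different groups. An analysis that ignores this counts each participant as a full independent observation and overstates the information in the trial.

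Neither technical phrase in the Statistical Plan cures it:

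- **Random intercept.** Read in the usual way, it belongs to the participant and handles repeated measures within a person. Even a group-level intercept would cancel from pre-to-post change, which is the outcome.
- **Robust errors.** They allow for correlation between participants only if the group is declared as the cluster.

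At stake are the primary interval and p-value, the secondary outcomes, the second-segment estimate and the comparison of segments. There is no multiplicity adjustment because there is a single primary endpoint, so the trial's claim rests on that one test being valid at its stated level.

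**Working it through.** **Inputs from the documents.** Nominal level 0.05 (taken as two-sided; the plan does not say); 1:1 allocation; group delivery; no group term. The plan gives no sample size, power or ICC figure to reproduce. At ICC = 0 the normal formula below returns 0.0500, as it should.

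**Assumptions, not in the documents.** Group size m = 6 or 8; 3 to 5 groups per arm; ICC of change 0.01 to 0.20; equal total variance in the arms; complete data.

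**Two readings of the unit of randomisation.**

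- A: whole groups were randomised and both arms are clustered.
- B: individuals were randomised and, in the first segment, only BIT+ is clustered.

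If whole groups were randomised but waitlist members do not interact, the answer lies between A and B.

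**Step 1: design effect (DE).**

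- DE(A) = 1 + (m − 1) × ICC
- DE(B) = [DE(A) + 1] / 2
- SE understatement = 1 − 1/√DE

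| m | ICC | DE(A) | SE understated | DE(B) | SE understated |
|---|---|---|---|---|---|
| 6 | 0.01 | 1.05 | 2.4% | 1.025 | 1.2% |
| 8 | 0.10 | 1.70 | 23.3% | 1.35 | 13.9% |
| 8 | 0.20 | 2.40 | 35.5% | 1.70 | 23.3% |

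**Step 2: type I error.** The large-sample formula is 2 × [1 − Φ(1.96/√DE)]. For example, with m = 8 and ICC 0.10 under A, 1.96/√1.70 = 1.50, which gives 13.3%. The simulation used 200,000 null trials per cell and a participant-level robust z-test on change. Ranges run over m = 6 and 8 and, for the simulation, 3 to 5 groups per arm.

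| ICC | A, formula | A, simulated | B, formula | B, simulated |
|---|---|---|---|---|
| 0 | 5.0% | 5.6-6.6% | 5.0% | 5.7-6.6% |
| 0.01 | 5.6-5.8% | 6.4-7.2% | 5.3-5.4% | 6.1-6.9% |
| 0.05 | 8.0-9.2% | 9.2-10.8% | 6.5-7.1% | 7.6-8.5% |
| 0.10 | 11.0-13.3% | 12.4-15.5% | 8.0-9.2% | 9.2-10.8% |
| 0.20 | 16.6-20.6% | 18.5-23.7% | 11.0-13.3% | 12.5-15.4% |

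The row at ICC = 0 shows 0.6-1.6 points of inflation from using a normal reference in a small sample. With a participant-level t-test instead, clustering alone gives 5.5-21.6% under A and 5.3-13.5% under B. A separate simulation (40,000 trials per cell, n − 1 variance divisor) gave values lower by less than 1 point.

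**Step 3: comparison of segments.** Everyone on both sides was treated in a BIT+ group, so the A figures apply under either reading.

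**Step 4: where the group effect must sit.** With 4 groups of 8 per arm under A (20,000 trials), a group effect on level only gives 5.8%, the same as no clustering. A group effect on change with ICC 0.10 gives 15.1%.

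**Step 5: would declaring the cluster be enough?** A cluster-robust error with a normal reference and no small-sample correction gives 11.7-18.6% under A and 8.1-13.7% under B. With this few groups it is not enough.

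**The case against.** The other side has several fair points.

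- **Silence is not proof.** The plan does not say that groups were ignored. True, but an analyst who follows the text would fit no group term, and that is what a plan is judged on.
- **The word group may simply mean arm,** since the same sentence goes on to speak of intervention and waitlist groups. That reading amounts to B, where BIT+ is still clustered. It does stand that the larger, A-type figures for the primary test need waitlist clustering, which the documents nowhere describe.
- **Under B, a treatment that does nothing to anyone creates no group effects,** so the type I error statement needs a null in which group effects exist but average to zero. This stands. The too-narrow interval does not need that condition. In the comparison of segments, equal mean change is fully compatible with real group effects.
- **The size is unknown.** ICC, group size and number of groups are all assumed, and the individual home sessions might lower the ICC. This stands.
- **The change comes late and replaces the estimator.** Recruitment ended in June 2019 and the document is dated November 2025. A mixed model keeps the missing-at-random handling, although a group-mean t-test does not by itself. Late timing is a reason for open labelling, not for keeping an analysis that leaves out the groups.

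**Conclusion.** The concern holds. The group is part of the allocation and the treatment but is missing from the analysis, under either reading of the unit of randomisation. The ambiguity changes the size of the error, not its direction.

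For any positive ICC of change, the interval is too narrow. On the assumed group sizes, the effect is negligible at an ICC of about 0.01 and material from about 0.05, where simulated type I error is 9.2-10.8% with both arms clustered and 7.6-8.5% with BIT+ alone. Confidence is high about the omission. The consequence cannot be sized without the group counts and the ICC, and the plan provides for reporting neither. Because the primary inference is affected, this should be corrected before that result is relied on.

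**What to change.** 1. State whether groups or individuals were randomised, and give the number and size of groups in each arm and segment.
2. In the primary, secondary and second-segment analyses and in the comparison of segments, put a group-level random effect on the change (group by time). Use it in both arms if groups were randomised. If individuals were, use it for BIT+ only in the first segment (a partially nested model), with cohort as a stratum.
3. Fit by REML with Kenward-Roger or Satterthwaite degrees of freedom. If whole groups were randomised, a t-test on group means is an alternative. Do not rely on a cluster-robust error with a normal reference if groups are few.
4. Report the ICC of change with its interval. Show the participant-level result beside the clustered one, and say when and why the clustered analysis was added.

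**Cost.** SAP wording and a re-run; group membership should be on record because the groups were run. The interval will widen. Under A with 3 to 5 groups per arm there are 4 to 8 degrees of freedom, so the critical value is 2.78 to 2.31 instead of 1.96. That alone widens the interval by 42% to 18% (2.78/1.96 = 1.42; 2.31/1.96 = 1.18). The group variance will be imprecise with so few groups.

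**Performance in simulation.** The group-mean t-test holds 4.9-5.1% under A. The partially nested Satterthwaite test stays slightly liberal, at 5.1-6.6%, under B. With the group variance truncated at zero, the tests give 3.0-5.6%.

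### Does the 20-visit list leave the waitlist arm without the end-of-wait score that the first-segment comparison needs?

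*Combined protocol and SAP*

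**What the plan says.** Under Methods, Procedures: "Participants made 20 study-related visits to the study site", itemized as "a baseline visit at the study start, 18 weekly visits for the BIT+ intervention, and a close-out visit", the last of these at the completion of the study. The list is not split by arm. The Objectives set an 18-week waitlist as the control condition, and the Scientific background says that waitlist participants were offered BIT+ afterwards.

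The Statistical Plan will "compare the change from the pre-to post-treatment assessment during the first segment of our study". The change in the outcome "will be modeled as the key dependent variable predicted by the treatment assignment status". For the period in which the waitlist arm receives BIT+, it says "We applied the same analytical strategy to analyze the data from the second segment of our study". It names SI-R total, SI-R response (a reduction of at least 14 points) and, among further outcomes, the SI-R subscales: "We will analyze several secondary outcomes including subscales of SI-R".

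On blinding, the Design section says that the facilitators could not be blinded and that "the independent evaluators who assessed home clutter levels were blinded to allocation". The Clutter Image Rating (CIR) is the only clutter instrument named, and it appears only in the eligibility criteria.

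**The concern.** The waitlist arm has to supply two changes: one over the wait and one over its own BIT+ course. That takes three scores, at about weeks 0, 18 and 36 (18 + 18 = 36). If baseline and close-out are the only assessments, and close-out comes after BIT+, the arm has two scores and the one at week 18 is missing. The SI-R total contrast, which carries the trial's hypothesis, would then have no control value. The missing-at-random assumption would not help, because the plan applies it to attrition and not to a score unscheduled for a whole arm.

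Clutter raises a related worry. It is the only assessment stated to be blinded, and blinding protects a treatment comparison chiefly in the first segment, where the arms differ in treatment. If clutter were reported only for the second segment or for pooled completers, it would be an uncontrolled change.

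**Working it through.** **1. Reproduce the stated count.** Inputs from Procedures: 1 baseline, 18 weekly visits, 1 close-out. 1 + 18 + 1 = 20, which matches the stated figure exactly.

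**2. What the first-segment model needs.** The fixed effects are intercept, group, time and group × time. The treatment effect is the last term:

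(BIT+ post − BIT+ pre) − (waitlist post − waitlist pre).

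With all four group-by-time cells the design matrix has rank 4 of 4, so the term can be estimated. Without the waitlist post cell the rank is 3 of 4, and it cannot. The end-of-wait score is therefore indispensable. The question is whether the documents imply that it was not planned.

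**3. What the visit list describes.**
- Procedures says the methods were those of the pilot apart from two changes, one to breaks in the weekly meetings and one to the timing of uncluttering. The Scientific background describes that pilot as open-label with N = 5. The waitlist is a larger departure than either change, yet it is not among them, and Procedures does not mention it.
- When describing the pilot's uncluttering schedule, Procedures places it at the end of the study, meaning the end of the treatment course. Close-out at study completion can be read the same way.
- The list does not say what was measured at any visit. It gives 18 weekly site visits against 16 weekly workshops, and the uncluttering sessions took place at home. So 18 − 16 = 2 weekly site visits have no stated content. A list this loose cannot show that there was no room for another assessment.

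**4. Does a third assessment break the count?** As a separate site visit it would give 20 + 1 = 21 for the waitlist arm. Taken at the first weekly visit, at home or remotely, it leaves the count at 20. The stated 20 is compatible with three assessments.

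**5. Could the close-out score be used by mistake?** Let B be the BIT+ effect, and W1 and W2 the changes from time alone over weeks 0–18 and 18–36. The intended contrast is (B + W1) − W1 = B. Using the week-36 waitlist score instead would give (B + W1) − (W1 + W2 + B) = −W2, so the BIT+ effect would cancel if it were equal in both segments. But this requires a second-segment score to serve as a first-segment outcome. The Statistical Plan confines the comparison to the first segment and treats the second separately, so an analyst who follows it does not make that substitution.

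**6. Clutter.** The visits counted are to the study site, so the list says little about when homes were rated. The secondary outcomes are introduced as several, with the SI-R subscales as examples. If clutter is among them, the plan's general model gives it the same first-segment contrast by assignment.

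**The case for a change.** The strongest case on the other side is textual. The visit list is stated for participants generally, its last item is tied to the completion of the study, and its items use up the total. No section states an end-of-wait assessment for any measure. A reader who takes the list literally has a control arm with no control score, and one sentence would settle the matter. An open outcome list also fixes neither the instrument nor the time points for the one assessment stated to be blinded.

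Part of this stands. The documents do not give assessment weeks by arm, do not say whether evaluator-rated clutter is an outcome, and do not say which instrument the evaluators used. A reader cannot confirm those facts from the text. It does not stand that the comparison is unplanned or lost, because the Statistical Plan specifies an analysis that needs the score, and nothing in Procedures rules it out.

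Writing the detail in now would also gain little. Recruitment ended in June 2019 and the document is dated November 2025. Naming clutter at this date would not make it pre-specified.

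**Conclusion.** No change to the plan follows. The visit arithmetic is correct at 20. The first-segment contrast is sound as the Statistical Plan states it, and the missing assessment weeks are a descriptive gap that an analyst fills in the only way the model allows, with a waitlist score taken before BIT+ begins. The effect on the planned estimate is nil. No bias or loss of power can be attached to the plan, since those would arise only under an analysis it does not propose.

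This rests on two assumptions: that the visit list describes one BIT+ course, and that waitlist participants were scored before starting BIT+. The documents support both readings but state neither. If the second were false, the arm comparison could not be estimated at all, and no rewording would restore it.

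### Does the plan leave the blinded home clutter rating without a place in the randomised BIT+ versus waitlist comparison?

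*Combined protocol and SAP*

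**What the plan says.** The Design section describes a 1:1 randomised comparison of BIT+ with a waitlist. It says that group facilitators could not be blinded and that "the independent evaluators who assessed home clutter levels were blinded to allocation". It gives no instrument or rating times for that assessment. The Clutter Image Rating appears only under Inclusion and Exclusion Criteria, as a lower limit of 4 for entry and an exclusion above 8.

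The Statistical Plan names SI-R total and a response of at least 14 points on it, then adds: "We will analyze several secondary outcomes including subscales of SI-R". For the first segment, "the change (slope) in the outcome will be modeled as the key dependent variable predicted by the treatment assignment status". For the second, the authors applied "the same analytical strategy to analyze the data from the second segment of our study, where the individuals assigned to the waitlist condition" go on to receive BIT+. They add that "we will compare the first and second segments in terms of the estimated changes under BIT+ treatment". The Scientific background mentions one further analysis: "the BIT+ completer sample was pooled to allow us sufficient sample size to estimate clinical benefits".

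The Design section justifies the waitlist as a way to treat everyone "while controlling for passage of time and allowing comparison to a prior study of BIT". It also says: "The trial was prospectively registered".

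**The concern.** Clutter is central to this trial. The Scientific background motivates BIT+ by the clutter that remains after existing treatments, and the added component is uncluttering practice in the home. It is also the one measure with stated protection against assessor bias, so one would expect the analysis section to name it.

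The document has several places where a clutter result could appear, and they are not equivalent. In the first segment it would be a randomised difference with blinded raters. In the second segment, or in the pooled completers, it would be a pre-to-post change with no untreated comparator, and the control for passage of time that justified the waitlist would be lost. If the clutter result came only from those analyses, a reader might credit it with the protection of the blinding statement. What is at stake is how a secondary clutter result may be described.

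**Working it through.** The document gives no sample size, effect size, standard deviation or dropout rate, and the point turns on none of them. The check is mainly one of reading the sections against each other.

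**1. Is clutter assigned to any analysis?** No. The Statistical Plan does not mention it, so it is assigned neither to the first segment nor to the uncontrolled analyses. The gap is silence; nothing misdirects the analyst.

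**2. What would an analyst do by default?** The blinding sentence stands in the Design paragraph on the randomised arms and refers to allocation. The first-segment model takes a generic outcome and regresses its slope on assignment. The secondary list is introduced as inclusive. Put together, these lead to clutter being analysed as BIT+ versus waitlist with the same mixed model as SI-R total.

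**3. What does each analysis estimate?** Let *d* be the mean change without BIT+ and *t* the BIT+ effect.
- First-segment difference: (*d* + *t*) − *d* = *t*.
- Second-segment or pooled change: *d* + *t*.

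This distinction is correct, but it holds for SI-R as much as for clutter. It describes uncontrolled changes in general and does not measure the missing link.

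**4. Does blinding to allocation lose all value outside the first segment?** No. Assume that BIT+ follows the waitlist without a gap and that both arms are rated at the end of the first segment. The waitlist arm's rating after BIT+ then falls at week 18 + 18 = 36. At week 18 a blinded evaluator does not know whether a home has just had BIT+ or the waitlist. That rating closes the BIT+ arm's change and opens the second-segment change. Let *r* be waitlist-arm completers divided by BIT+-arm completers. The values below 1 are assumed.

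| *r* | Pooled changes from second segment, *r*/(1 + *r*) | Pooled changes closing at the masked week-18 rating, 1/(1 + *r*) |
|---|---|---|
| 1 | 50.0% | 50.0% |
| 0.75 | 42.9% | 57.1% |
| 0.5 | 33.3% | 66.7% |

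Only the week-36 rating clearly lacks masking to treatment received. Having no untreated comparator and having no rater masking are separate matters; the first is complete in the pooled sample, the second only partial.

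**5. Is the first segment the only place where allocation groups are contrasted?** Not quite. The planned comparison of segments sets the BIT+ arm against the former waitlist arm, so it also contrasts allocation groups, although both sides have received BIT+. The accurate statement is that the first segment is the only randomised BIT+ versus untreated comparison.

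**6. Does the text invite the misreading?** No section calls a second-segment or pooled clutter result blinded. The sentence on pooling does not mention clutter, and the Statistical Plan describes no pooled completer analysis.

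**The case for a change.** The strongest reply is that an open list commits the authors to nothing. It allows clutter to be reported from the randomised segment, from the pooled sample only, or not at all. The pilot procedures, which the Procedures section adopts with two exceptions, are an unlikely source for the answer, since the pilot was open-label with five participants and had no between-arm comparison. The Procedures section also lists a baseline visit, 18 weekly visits and a close-out visit, with no assessment at the end of the waitlist, and a controlled clutter result needs one.

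Part of this stands. The instrument and rating times are missing, and a fuller plan would have named clutter among the secondary outcomes. Two things limit its force. The visit list counts attendance at the study site, so it says nothing about ratings made in the home; and the first-segment comparison of SI-R itself presupposes an end-of-segment assessment in the waitlist arm. The trial was also registered in advance, so the detail may sit in a record outside this document, and the document alone cannot show that it was never specified.

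**Conclusion.** No change to the plan follows. The Statistical Plan omits the name, instrument and timing of the blinded clutter rating, but its generic first-segment model and open secondary list lead an analyst to the right comparison. Any second-segment or pooled clutter change would be uncontrolled, and the plan's own description of those analyses already makes that plain.

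The gap has no numerical size: the pooled shares above rest on assumed completion ratios and illustrate only that rater masking is not wholly lost. The primary analysis of SI-R total is unaffected. Added wording would gain little. It would record detail without altering the analysis, and in a document dated November 2025 it could not restore prespecification for a trial that stopped recruiting in June 2019.

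The conclusion assumes that clutter was rated in both arms at the end of the first segment, which the Design section suggests but does not confirm. Without those ratings there would be no blinded controlled clutter result to report, and new text could not create one.
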